HOPE	Hemodialysis Pain Reduction Effort
IRB	Institutional Review Board
ICC	intra-cluster correlation coefficient
IVR	interactive voice response
MME	morphine milligram equivalents
MOP	Manual of Procedures
MSPSS	Multidimensional Scale of Perceived Social Support
NIDDK	National Institute of Diabetes and Digestive and Kidney Diseases
NIH	National Institutes of Health
NSAIDS	non-steroidal anti-inflammatory drugs
OHRP	Office of Human Research Protections
OUD	opioid use disorder
PA	physician assistant
PCS	Pain Catastrophizing Scale
PCST	pain coping skills training
PGIC	Patient Global Impression of Change
PHI	protected health information
PHQ-9	Patient Health Questionnaire – 9
PRO	patient reported outcome
PROMIS	Patient-Reported Outcomes Measurement Information System
QOL	Quality of Life
MQOL	McGill Quality of Life
SAE	serious adverse event
SDRC	Scientific and Data Research Center
SIS	Single-item scale
SSRIs	selective serotonin reuptake inhibitors
SNRIs	serotonin-nor-epinephrine reuptake inhibitors
SUD	substance use disorder
TAPS	Tobacco, Alcohol, Prescription medication, and other Substance use Tool
TLFB	Timeline Followback
UPenn	University of Pennsylvania
U.S.	United States

1. STUDY SUMMARY

1.1. Synopsis

Title	HOPE Consortium Trial to Reduce Pain and Opioid Use in Hemodialysis
Short Title	HOPE Trial
Study Description	HOPE is a randomized clinical trial that will evaluate approaches to reducing pain and opioid use among patients with chronic pain who are receiving maintenance hemodialysis for end-stage renal disease. The hypotheses are: 1) pain coping skills training is effective at reducing pain and opioid use, and 2) buprenorphine is acceptable and tolerable as an approach for managing opioid physical dependence.
Objectives	
Primary Objective
 
• To evaluate the effectiveness of pain coping skills training compared with usual care for reducing pain interference (primary outcome), and for improving other pain outcomes, opioid use, and associated conditions (all secondary outcomes) among patients with end-stage renal disease receiving treatment with maintenance hemodialysis 
Secondary Objective
 
• To explore acceptability, tolerability, and efficacy of buprenorphine in a subgroup of trial participants prescribed moderate to high-dose long-term opioid therapy for chronic pain
Primary Outcome	Pain interference as measured by the Brief Pain Inventory Interference Scale
Secondary Outcomes	
• Pain intensity• Pain catastrophizing• Opioid use• Composite of pain interference and opioid use• Quality of life• Physical functioning• Depression• Anxiety• Coping• Self-efficacy• Sleep quality• Fatigue• Other symptoms• Satisfaction with treatment• Social support• Family intrusion

	
• Discrimination• Falls• Hospitalizations• Death• Buprenorphine acceptability• Buprenorphine tolerability
Study Population	640 patients being treated with maintenance hemodialysis for end-stage renal disease who have chronic pain, at least 300 of whom have prescription opioid use.
Phase or Trial Type	Effectiveness (PCST intervention); Exploratory (buprenorphine intervention)
Description of Sites/Facilities Enrolling Participants	
Participants are enrolled from multiple dialysis units affiliated with the following 8 Clinical Centers, some of which involve collaborations across multiple medical centers:
 
• Hennepin Health Care• Massachusetts General Hospital• New York University• University of Illinois-Chicago• University of Pittsburgh; University of Pennsylvania• University of Washington; University of New Mexico; Rogosin Institute• Vanderbilt University Medical Center; West Virginia University• Yale University; Multiple Veterans Affairs Healthcare Systems 
The Scientific and Data Research Center is based at the University of Pennsylvania.

Description of Study Intervention	
1. Pain Coping Skills Training (PCST): Participants will complete a structured, standardized, interactive program designed to reduce pain interference, opioid use, and comorbid symptoms of depression, anxiety, and sleep disturbance. The program is adapted for the hemodialysis patient population, and is delivered using live coaches via video telehealth and with interactive voice response via telephone.2. Usual Care: Participants will be given educational materials and resources about alternatives to opioid pain medications. These materials will also be provided to participants in the PCST group.3. Buprenorphine: In a second phase of the trial, participants in both the PCST and Usual Care groups who meet eligibility criteria, including use of moderate to high-dose prescribed opioid therapy, will be offered buprenorphine as an alternative to a full-agonist opioid pain medication.
Study Duration	44 months
Participant Duration	36 weeks

[figure not shown]

1.3. Study Schema

2. INTRODUCTION AND RATIONALE

2.1. Study Rationale

With the recognition that many patients with end-stage renal disease (ESRD) prioritize how they feel and function over how long they live, there has been increased effort to address the tremendous symptom burden that accompanies ESRD.¹ Pain is among the most common of these symptoms with approximately 60% of dialysis patients reporting pain that is usually described as moderate or severe.² The causes and types of pain in this patient population are numerous and medical management is complicated by altered pharmacokinetic and pharmacodynamic properties of analgesic agents in the setting of kidney failure. Due to both the high prevalence of pain and the limited options for its management, use of opioid medications is common in this population. In 2010, as many as 20% of hemodialysis patients in the United States (U.S.) received prescribed opioids for 90 days or longer.³ Long term opioid therapy is of questionable benefit for chronic pain,^{4,5} and, among the general population, is associated, in a dose-dependent manner, with an increased likelihood of serious harms including declining functional status, infection, hypogonadism, overdose, and opioid use disorder (OUD).^{6,7} Among hemodialysis patients, long term opioid use is associated with increased rates of falls, hip fractures, hospitalizations, dialysis withdrawal, and death.^{3,8} Patients treated with hemodialysis generally have low levels of physical activity and high rates of insomnia and depression,⁹ all of which can exacerbate chronic pain, complicate its management, and be potentiated by opioid use.¹⁰ Non-pharmacologic approaches such as cognitive behavioral therapy, mindfulness, and acceptance and commitment therapy, have demonstrated efficacy for chronic pain in the general population, but have not been studied in ESRD.

Buprenorphine, a partial opioid agonist with an improved safety profile compared to other opioids, may be an effective option for reducing opioid use among patients treated with hemodialysis, but there is limited experience with this drug in the ESRD population. Thus, the primary objective of this 36-week trial is to evaluate the effectiveness of a cognitive behavioral therapy-based intervention called pain coping skills training (PCST) for improving pain and reducing opioid use among patients on hemodialysis with chronic pain. A secondary objective is to explore acceptability, tolerability, and efficacy of buprenorphine among patients who are using prescribed moderate to high-dose opioid therapy.

2.2. Background

2.2.1. Prevalence of Pain among Patients Treated with Hemodialysis

In the U.S. chronic pain has a prevalence of 11% among adults and was estimated in 2016 to have an annual cost of \$635 billion.¹¹ Due to a high comorbidity burden, chronic pain is even more common among patients undergoing treatment with maintenance hemodialysis.^{12 13} More than half of hemodialysis patients have diabetes mellitus,¹⁴ often with accompanying painful neuropathy, and most patients have ESRD-associated mineral metabolism disorders that predispose to chronic musculoskeletal pain,¹⁵ and to a fracture risk that is 2- to 4-fold higher than that for the general population.¹⁶ Falls are also common among hemodialysis patients; recent reports indicate that 25-30% of hemodialysis patients experience at least one fall per year and 57% of these individuals reported multiple falls.¹⁷

Pain in the setting of ESRD and hemodialysis has some key differences from that experienced by the general population. In addition to chronic pain, patients often experience acute pain associated with recurring hemodialysis sessions (typically 3 per week). Sources of hemodialysis-associated pain include severe muscle cramping resulting from fluid removal, needle infiltrations, vascular steal syndrome and other complications of hemodialysis vascular access, and a “washed out” feeling with substantial fatigue and headaches that may persist for up to 12 hours after dialysis sessions. One recent systematic review estimated that 33-82% and 21-92% of dialysis patients have acute and chronic pain, respectively.¹⁸ An earlier systematic review quantified this as a mean prevalence of pain of 47% across 60 studies, with pain during the hemodialysis treatments, including vascular access pain, headache, neuropathic pain, and musculoskeletal pain, occurring most frequently.¹²

2.2.2. Complexity of Pain Management among Patients Treated with Hemodialysis

Pharmacologic options to treat pain are limited for patients receiving maintenance dialysis because of a difficult balance between efficacy and safety for many types of medications (see **Table 2.1**). The high risk-to-benefit ratio results from reduced clearance of agents that are metabolized by the kidneys and from side effects that are of particular significance in the presence of kidney failure. Despite limited evidence for efficacy,¹⁹ long-term opioid therapy, defined as ≥ 90 days of opioid analgesics, has emerged as a dominant treatment paradigm for chronic pain, particularly among maintenance hemodialysis patients.³ The challenges associated with long-term use of opioid medications, discussed in **Section 2.2.3**, have resulted in a critical need in the dialysis population for better pharmacologic strategies as well as approaches that combine pharmacologic and non-pharmacologic interventions to reduce pain and its deleterious effects.

Table 2.1. Systemic Pharmacologic Options for Pain in Hemodialysis: Benefits and Limitations^{20, 21}

Class	Benefits	Limitations
Non-steroidal anti-inflammatory drugs (NSAIDS)	Effective pain control; inexpensive; no central nervous system effects	May accelerate loss of residual kidney function; gastrointestinal bleeding
COX-2 Inhibitors	Effective pain control; no CNS effects	May accelerate loss of residual kidney function; pro-thrombotic
Acetaminophen	Safe; inexpensive	Often insufficient analgesia; liver toxicity
Tricyclic antidepressants	Likely effective for treating neuropathic pain	Anticholinergic adverse effects, particularly in the elderly
Selective serotonin reuptake inhibitors / serotonin-nor-epinephrine reuptake inhibitors	May be effective for treating neuropathic and headache pain	Dosing considerations for some agents; may worsen restless leg syndrome; QT prolongation with some agents
Gabapentin / Pregabalin	Likely effective for neuropathic pain	High toxicity risk including mental status changes, somnolence, and hypotension
Opioids	May be effective for treating pain in some patients (mixed evidence);	Addiction potential; constipation, mental status changes, somnolence, respiratory depression; mixed evidence for efficacy for chronic pain

2.2.3. Potential Harms from Long Term Opioid Therapy

In the non-dialysis population, observational data and limited clinical trial data suggest that long-term opioid therapy is associated with potential harms without significant improvements in chronic pain. In addition to a higher risk of overdose death among long-term opioid recipients,²² accumulating data show dose-dependent associations with hypogonadism, infection,⁶ osteoporosis, falls, fractures, motor vehicle accidents, opioid use disorder (OUD), and intermittent withdrawal symptoms,⁷ and, additionally, among hemodialysis patients, with increased rates of hospitalizations, dialysis withdrawal, and death.³ For the general population, the Centers for Disease Control and Prevention (CDC) recommends using non-opioid medications instead of opioids for chronic pain. For patients already taking opioids, the CDC recommends that providers use caution if increasing opioid doses above 50 MME/day and avoid dose escalations to beyond 90 MME/day.²³ For the dialysis patient population, data to guide opioid dosing and alternative pain management strategies are lacking.²¹ For example, because of its hepatic metabolism and elimination, methadone is a favored opioid in the setting of kidney failure;²⁴ however, methadone has multiple drug interactions and prolongs the QT interval which may have important implications given the high rates of sudden cardiac death among hemodialysis patients.

2.2.4. The Need for Non-Pharmacologic Approaches to Pain Management and Opioid Reduction in the Setting of Maintenance Hemodialysis

Individuals receiving maintenance hemodialysis are an exceedingly vulnerable population. Mortality rates are similar to those for metastatic cancer,²⁵ the burden of pain, prevalence of frailty, and rates of physical and cognitive impairment are high, and there are few well-studied strategies for managing symptoms. As is evident in **Table 2.1**, pain management is challenging in the setting of kidney failure. Non-steroidal anti-inflammatory drugs are often contraindicated because of the need to maintain residual kidney function and the risk of gastrointestinal bleeding, and the use of other agents, such as gabapentin and pregabalin,²⁶ is limited by toxicities including orthostasis, encephalopathy, somnolence, and falls. Many opioids are metabolized and cleared differently when kidney function is reduced, increasing the risk of adverse effects of some agents. Patients with dialysis-dependent ESRD may be more vulnerable to the neurocognitive, endocrine and infectious complications of opioids, but they may also be more vulnerable to the complications associated with non-opioid based pain regimens and, in the absence of pain control, may become increasingly debilitated. Accordingly, safely minimizing the toxicities of pain management strategies while maximizing overall levels of functioning is a critical goal for this patient population. These complexities underscore the need for targeted strategies to incorporate non-pharmacological approaches to pain management.

2.2.5. Rationale for a Pain Coping Skills Training Intervention to Address Pain and Opioid Use

Cognitive behavioral therapy directed at pain coping skills has a strong evidence base and is among the most widely studied non-pharmacological treatments for chronic pain.²⁷ Providing cognitive behavioral coping skills training is an attractive adjunct or alternative to pharmacological treatments because its effects can persist after treatment is discontinued without the negative side effects and potential harms of pharmacological treatments such as opioids. The goal of a cognitive behavioral pain coping skills intervention is to help patients develop skills to manage pain, and its associated disability and emotional distress, as a means to improve functioning and quality of life.²⁸ Skills include reframing maladaptive cognitive processes (e.g., catastrophizing)

and promoting adaptive behaviors (e.g., relaxation). Cognitive behavioral interventions have been recommended by the CDC²³ and American College of Physicians (ACP)²⁹ as a first-line treatment to reduce pain and improve function.

Newer treatments such as mindfulness and acceptance and commitment therapy share commonalities in their underlying rationale and treatment strategies with standard cognitive behavioral therapy. Because of these commonalities and lack of single universally accepted protocol for these treatments for pain, many interventions for chronic pain combine techniques from all of these treatments.

2.2.5.1. Efficacy of Interactive Voice Response for Chronic Pain Cognitive Behavioral Interventions

In addition to providing pain coping skills training through telehealth-delivered real-time sessions between a coach and a patient, the cognitive behavioral intervention for this trial includes an interactive voice response (IVR) component that is based on the recently developed and tested COPES (Cooperative Pain Education and Self-Management) program.³⁰ In a non-inferiority trial that compared an in-person cognitive behavioral intervention to COPES in a non-ESRD patient population, post-treatment statistically significant improvements in physical functioning, sleep quality, and physical quality of life relative to baseline occurred with both treatments, with no significant advantage for either treatment.³⁰ Additionally, patients were equally satisfied with COPES and the in-person intervention. Importantly, work by Naylor and colleagues demonstrated that IVR-based booster sessions, similar to those that will be used in this trial, following a traditional cognitive behavioral intervention produced maintenance of treatment gains and continued reduction in opioid medication use.³¹

The IVR treatment infrastructure that has been developed and tested in prior trials will provide foundational resources for this trial. In prior studies, participants completed 85-90% of scheduled daily calls. The COPES manual includes an extensive library of feedback scripts that have been refined based on post-treatment participant interviews and feedback with participants from the original COPES trial. These feedback scripts will serve as the basis for the personalized feedback in the planned IVR booster intervention.

2.2.5.2. Adaptation of Pain Coping Skills Training Interventions to the Hemodialysis Population

Patients undergoing hemodialysis have high rates of depression, and the presence of depressive symptoms is known to be associated with dialysis withdrawal, hospitalization, mortality, and non-adherence with dialysis treatments.³²⁻³⁴ Additionally, low rates of physical activity, poor sleep, and quality of life are well-documented in this population.³⁵⁻³⁷ Cognitive behavioral skills may be effective for improving depression, quality of life, and sleep, and increasing physical activity and adherence behaviors among patients treated with hemodialysis.³⁸ For the HOPE Trial, the Pain Coping Skills Training (PCST) intervention will retain the critical components of traditional behavioral pain management skills but will be expanded to include skills for mood regulation, sleep improvement, and anxiety management, all core issues for this patient population. A focus will be on highlighting how these conditions and their treatment overlap and interact, e.g., walking improves pain and physical function, or cognitive restructuring can address pain catastrophizing as well as beliefs that impede hemodialysis adherence or maintain depressive symptoms. Additionally, the intervention will promote use of

skills such as guided mindfulness and progressive muscle relaxation during hemodialysis sessions, a setting well-suited for these types of interventions.

2.2.6. Rationale for a Buprenorphine Intervention to Address Opioid Physical Dependence in Hemodialysis Patients

Buprenorphine is a partial opioid agonist with analgesic properties similar to those of full-agonist opioids. Various formulations of buprenorphine are available for the treatment of opioid use disorder and for pain. Because buprenorphine causes less respiratory depression than full agonist opioids, it is considered to be safer and is designated as a schedule III controlled substance, in contrast to schedule II full agonists such as oxycodone, hydrocodone and others.^{39, 40} Among patients on long-term opioid therapy for chronic pain, higher prescribed opioid daily doses (compared with lower daily doses) are associated with worse pain-related function and more frequent adverse outcomes. Limited evidence suggests that opioid dose reduction can improve pain, function, and quality of life; however, physical dependence makes it difficult for many patients prescribed long-term opioids to reduce their opioid use. Buprenorphine addresses physical dependence by preventing withdrawal symptoms and reducing cravings. Patients who have transitioned from high-dose opioids to buprenorphine often have improved pain/function and decreased opioid-related adverse effects.^{41, 42} In a large controlled case series, buprenorphine was effective for successful discontinuation of full-agonist opioids by patients on long-term opioid therapy for pain; due to marked physical opioid dependence, patients in this study used higher dose buprenorphine formulations approved for treating opioid use disorder,⁴³ as opposed to the lower dose formulations approved for pain. Benefits of switching from full-agonist opioids to buprenorphine are hypothesized to be due to effective management of physical dependence, which allows patients to more easily reduce their overall opioid use. Buprenorphine may also have fewer adverse cognitive and emotional effects than other opioids. Patients receiving maintenance hemodialysis for kidney failure may be especially vulnerable to adverse effects associated with use of long-term opioids and may experience these adverse effects at lower daily dosages than other patients. Thus, strategies are needed to help this patient population reduce opioid use and, ultimately, reduce pain interference and opioid adverse effects. The HOPE Consortium trial will evaluate, in an exploratory manner, the acceptability, tolerability, and potential efficacy of buprenorphine for physical dependence on opioids in hemodialysis patients on moderate to high-dose long-term opioid therapy.

2.2.6.1. Buprenorphine Pharmacokinetics, Pharmacodynamics, and Toxicology

Buprenorphine taken orally undergoes extensive first-pass metabolism but its bioavailability with sublingual administration makes this a feasible route of administration. The mean time to maximum plasma concentration of buprenorphine following sublingual administration is variable, ranging from 40 minutes to 3.5 hours. Buprenorphine has a large volume of distribution and is highly protein bound (96%). The drug is extensively metabolized by N-dealkylation to norbuprenorphine, primarily through cytochrome P450 (CYP) 3A4 (i.e., liver, not renal, metabolism). The terminal elimination half-life of sublingually administered buprenorphine is 22 to 44 hours. Approximately 10-30% of buprenorphine is excreted in the urine. Some formulations of buprenorphine include naloxone as a deterrent to misuse via injection, but naloxone is inert when buprenorphine/naloxone is used as directed. Naloxone does not appear to influence the

pharmacokinetics of buprenorphine when the combination buprenorphine/naloxone product is taken as prescribed (sublingually). Buprenorphine crosses the placenta during pregnancy and also crosses into breast milk. It is not necessary to modify dosing of buprenorphine in kidney failure, and the safety of buprenorphine in ESRD and compatibility with hemodialysis are established.^{44,45} The half-life of buprenorphine may be prolonged in individuals with severe chronic liver disease because of reduced CYP3A4 activity. Buprenorphine is not removed by dialysis.⁴⁵

2.3. Risk / Benefit Assessment for the HOPE Trial Interventions

2.3.1. Known Potential Risks of Trial Interventions

The PCST intervention may increase distress for participants if sensitive topics are raised during the telehealth or IVR sessions. All prescribing decisions for participants will be made by the treating physicians rather than by the research team. Participants in both the PCST and Usual Care groups may have adverse effects from the non-opioid pain medications that are prescribed by treating (non-study) clinicians during the course of the study. Patients may experience withdrawal symptoms and other temporary discomfort due to reducing opioid doses, switching from one opioid medication to another, or transitioning to non-opioid medications. Because opioids may reduce the symptoms of restless leg syndrome in hemodialysis patients, reducing or discontinuing opioids may worsen this condition. Intervention clinicians will educate participants about withdrawal symptoms, take precautions to prevent withdrawal, and manage symptoms if they occur.

Common adverse effects of buprenorphine, the Phase 2 intervention, are similar to those of other opioids and include dizziness, headache, sedation, dry mouth, mouth numbness, constipation, insomnia, abdominal pain, drowsiness, fatigue, and numbness or tingling. An FDA report issued on January 12, 2022 identified dental issues such as tooth decay, cavities, oral infections, and loss of teeth, as newly recognized possible adverse effects of buprenorphine delivered via buccal or sublingual approaches. The FDA advises that these dental problems have been reported even in patients with no history of dental issues. The risk of these dental problems can be reduced by rinsing the mouth with water after using the drug, waiting at least an hour before teeth brushing, visiting a dentist shortly after starting buprenorphine, and having regular dental checkups. The FDA maintains that despite these risks, the benefits of buprenorphine medicines clearly outweigh the risks. As for all opioids, additive or synergistic interactions can occur between buprenorphine and central nervous system depressants including benzodiazepines and alcohol. Active, untreated substance use disorder is an exclusion criterion for the trial. Study investigators will educate participants eligible for the buprenorphine intervention about withdrawal symptoms, take precautions to prevent withdrawal, and manage symptoms if they occur.

The trial will not exclude people who are pregnant. Pregnancy is rare in patients undergoing maintenance hemodialysis. The PCST intervention does not require any specific medications or activities with pregnancy-associated risks, and for participants who are pregnant, lactating, or could possibly be pregnant, contraindicated medications will not be recommended by the research teams. People who are pregnant or people with child-bearing potential who are not willing to use acceptable forms of contraception will not be eligible for the buprenorphine intervention (**see Study Schema in Section 1.2**) since opioid withdrawal during pregnancy may increase the risk of miscarriage and preterm labor.

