2.3.3. Assessment of the Balance between Risks and Benefits

Risks of the trial interventions, described above, are similar to those in routine clinical care. Benefits and risks of recommended therapies will be discussed with patients as in clinical practice. To address the potential for increased distress from discussing sensitive topics in the PCST arm, the PCST coaches will be trained to manage such distress in accordance with accepted standard practices, and there will be a protocol in place for protective transfer should greater intensity of services be indicated. Buprenorphine is an FDA-approved medication for which there is more than 15 years of post-marketing data, and a risk profile that is similar among patients with and without impaired kidney function. Buprenorphine is a schedule III controlled substance, meaning its risk for abuse is considered by the DEA to be lower than the risk with the opioid medications likely to be used by patients enrolled in the trial (mostly schedule II opioids). Eligibility for the buprenorphine component of the trial intervention will be based on specific criteria assessed at Week 24 and use of buprenorphine will require additional informed consent.

Overall, the benefits of trial participation outweigh the risks based on the following considerations: 1) there are substantial potential benefits including improved pain management, decreased opioid-related adverse effects, and improved safety, and 2) the known risks will be minimized through individualized care decisions consistent with standards of care.

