7.4.2. Contacts with the Research Team (Weeks 4, 8, 12, 16, and 20)

Participants in both randomized groups will be contacted by research coordinators either in person or by telephone every 4 weeks during Phase 1. These contacts will be used for the following:

- Ascertainment of hospitalizations (secondary outcome)
- Ascertainment of falls (secondary outcome)
- Ascertainment of Adverse Events of Interest and SAEs
- Documentation of any change in the participant's opioid prescriber(s)
- Documentation of non-opioid analgesics, antidepressants, anxiolytic and sedatives/hypnotics
- Review of concomitant medications with documentation of initiation of new medications or discontinuation of prior medications
- Documentation of use of non-study behavioral or other non-pharmacologic treatments for pain
- Scheduling of Week 12 or Week 24 CATI calls

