9.2. Adverse Events of Interest

The following adverse events are anticipated in patients with chronic pain, opioid use, or treatment with the trial interventions, and will be considered AEs of Interest.

- Development of suicidality – based on response to question 9 of the PHQ-9
- Development of opioid use disorder or other substance use disorder
- Adverse effect from a medication started during the trial (including buprenorphine) to treat pain, opioid dependence, depression, or anxiety
- Falls
- Withdrawal symptoms
- Dental events in participants who have switched to buprenorphine

AEs of Interest will be ascertained during the contacts between the research coordinator and the participant that occur every 4 weeks through specific questioning and, as appropriate, by review of medical records. Information about the events will be recorded on the Adverse Event of Interest case report form (CRF) and entered into the data management system.

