10.4. Safety Analyses

Proportions of participants with at least one adverse event and rates of adverse events will be determined. Differences between the PCST and Usual Care groups in the proportions and the rates will be compared using logistic regression models and Poisson regression models, respectively, adjusting for baseline measures. For participants who switch to buprenorphine, adverse events occurring during the buprenorphine phase (Weeks 24-36) will also be summarized.

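### Two harms named in Section 2.3.1, PCST session distress and worse restless legs, are not AEs of Interest, so non-serious cases may be missed or captured unequally before the pooled comparison in Section 10.4

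*Combined protocol and SAP*

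**What the plan says.** Section 2.3.1 lists the known risks of the trial interventions. On PCST it states: "The PCST intervention may increase distress for participants if sensitive topics are raised during the telehealth or IVR sessions". On opioid reduction it names withdrawal and adds: "Because opioids may reduce the symptoms of restless leg syndrome in hemodialysis patients, reducing or discontinuing opioids may worsen this condition".

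Section 9.2 introduces its list as events "anticipated in patients with chronic pain, opioid use, or treatment with the trial interventions, and will be considered AEs of Interest". The six items are suicidality (from PHQ-9 question 9), opioid or other substance use disorder, adverse effects of a medication started during the trial, falls, withdrawal symptoms, and dental events after a switch to buprenorphine. They are found by specific questioning every four weeks and, as appropriate, by record review.

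The contact schedule in Section 7.4.2 reads "Ascertainment of Adverse Events of Interest and SAEs". Sections 4.1, 7.5.2 and 14.2 set the same scope. For session distress, Section 2.3.3 says that coaches will be trained to manage it and that "there will be a protocol in place for protective transfer should greater intensity of services be indicated". It states no step for recording either as an adverse event.

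Section 10.4 determines the proportion with at least one adverse event and the adverse event rate, and says: "Differences between the PCST and Usual Care groups in the proportions and the rates will be compared". It specifies no by-arm comparison of individual event types.

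**The concern.** Section 9.2 presents its list as the events anticipated with the interventions, yet two risks that Section 2.3.1 anticipates are not on it. An unlisted, non-serious event has no stated prompt at any contact.

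Both harms bear on the randomised comparison. Only PCST has sessions. PCST also includes motivational interviewing aimed at opioid reduction for participants with recent or current use (Section 6.1 and Table 6.1), and at least 300 participants are to be in that subgroup (Section 5.3). If PCST reduces opioid use, restless legs could worsen more in that arm.

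Unprompted capture need not be even: PCST participants have a coach who may notice and pass on distress, and Usual Care participants do not. A report of no excess adverse events with PCST would then rest partly on questions that were not asked.

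**Working it through.** **1. Each harm traced through the plan.**

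| Harm in 2.3.1 | AE of Interest in 9.2? | Other route into the data |
|---|---|---|
| PCST session distress | No; suicidality covers the severe end only | SAE if serious; PHQ-9 and GAD-7 at Weeks 0, 12, 24, 36 as secondary outcomes; IVR stress and anxiety data, which Section 6.1.5.1 excludes as outcomes |
| Worse restless legs after opioid reduction | No; the medication item covers only drugs started during the trial | Section 9.1.4 if pre-existing and worse; possibly withdrawal symptoms (not defined) or the Dialysis Symptom Index (items not given) |
| Withdrawal | Yes | – |
| Effects of newly started medication | Yes | – |
| Dental events on buprenorphine | Yes, in switchers | – |

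So 0 of the 2 harms at issue are among the 6 listed items, while the other three in the table are listed.

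**2. Scope of collection against scope of analysis.** Sections 4.1, 7.4.2, 7.5.2, 9.2 and 14.2 collect AEs of Interest and SAEs. Section 9.1.1 defines adverse events broadly, Section 9.1.5 says adverse events must be tracked and reported, Section 9.1.4 records worsened pre-existing conditions, and Section 10.4 analyses adverse events without restriction. The analysis is worded more widely than the prompted collection that feeds it.

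**3. Why a mean change does not settle the matter.** PHQ-9 and GAD-7 are compared by arm as changes in a mixed model. Assume that a share p of PCST participants worsens by 5 PHQ-9 points and the rest improve by 1 (assumed values):

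mean change = (1 − p)(−1) + 5p = −1 + 6p

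- p = 5%: −0.7
- p = 10%: 0.9 × (−1) + 0.1 × 5 = −0.4
- p = 15%: −0.1

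The mean still shows improvement until p reaches 1/6, about 17%.

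**4. What a by-arm proportion worsened could show.** The target is 640, so 320 per arm. With the 20% attrition of Section 10.2.1, 320 × 0.8 = 256 are followed. Ignoring site clustering:

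SE = √[p₁(1 − p₁)/256 + p₂(1 − p₂)/256]; half-width = 1.96 × SE; power = Φ((p₁ − p₂)/SE − 1.96)

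| Assumed PCST vs Usual Care | SE | 95% CI half-width | Power |
|---|---|---|---|
| 5% vs 2.5% | 0.0168 | 3.3 points | 32% |
| 10% vs 5% | 0.0232 | 4.5 points | 58% |
| 20% vs 10% | 0.0313 | 6.1 points | 89% |

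Section 10.4 states no figure of its own, so there is none to reproduce.

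**The case against.** A reader might infer that these harms are never recorded and that the safety comparison cannot show them. The documents do not support that. Section 9.1.4 would record worsening of pre-existing restless legs, Section 10.4 is not limited to AEs of Interest, and suicidality captures severe distress. Mood and anxiety are also compared between arms with masked data. What stands is incomplete and possibly uneven capture of non-serious cases.

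A reader might also infer that the plan ignores its predicted harms generally. It does not: withdrawal, effects of new medication and dental events are all listed.

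Three further objections have force:

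- Session distress cannot be a between-arm rate, because only PCST has sessions. It can only be described within that arm.
- A PHQ-9 or GAD-7 change at Weeks 12 and 24 measures sustained mood or anxiety, not a distressing session. The table proposed here must say so.
- Recording steps may be in the Manual of Procedures, which is not available here, and the amendment dates (Section 12, to July 2023) suggest that new questions could come too late for many participants. That favours the parts of the fix that use existing data.

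The item "Dental events in participants who have switched to buprenorphine" might prompt a call for a comparison with non-switchers. Phase 2 is exploratory and single-group. Section 10.3 expects at least 40 eligible, and at 25% uptake Table 10.6 gives 10 initiators. With no events in 10, the exact 95% upper limit is 1 − 0.025^(1/10), about 31%. Eligible non-switchers are self-selected. I would not press the dental comparison.

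**Conclusion.** The point holds as a gap in systematic ascertainment and reporting of two named harms when they are non-serious. It does not affect the primary efficacy analysis. It limits what a finding of no excess adverse events with PCST could mean, because a pooled any-event proportion or rate would not reveal whether these two had been sought.

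The size of any missed harm cannot be estimated from the documents. The rates and score changes in the working are assumptions. They show only that average improvement is compatible with a worsening minority, and that the existing data could give a signal of moderate precision. Whether restless legs is already covered by the Dialysis Symptom Index or by withdrawal symptoms cannot be settled from the text. The change is worth making because it is cheap.

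**What to change.** 1. **Section 10.4, existing data.** Prespecify a descriptive safety outcome: the proportion in each arm whose PHQ-9 or GAD-7 worsens from baseline to Weeks 12 and 24 by a threshold fixed before unblinding, with the difference and 95% CI, from the masked CATI data. State that it captures sustained mood or anxiety worsening, not transient session distress. Use observed participants as the denominator and show the number missing. Carrying baseline forward, as Section 10.6 does for a missing Week 12 primary outcome, would count missing participants as not worsened; with 20% missing, 10% would read as 0.8 × 10% = 8%.
2. **Section 9.2.** Add new or worse restless legs, asked identically in both arms at the existing four-weekly contacts. If participants are too far along, name an already collected PRO item that serves the purpose. Have coaches log session distress and protective transfers, reported descriptively for PCST only.
3. **Section 10.4, wording.** Report each AE of Interest by arm as well as the pooled rate. State whether adverse events means all of them or only AEs of Interest and SAEs, and align Sections 9.1.4, 9.1.5 and 7.4.2 with the answer.

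The cost is extra tables, one added question at contacts already held and a short coach log. The downside is slightly longer contacts and a slightly higher recorded adverse event count. If the question starts mid-trial, report the date so that the change in capture is visible.
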